5.8 Appendix D: Subject-reported Outcome Forms/Instruments

5.8.3 Modified Migraine Disability Assessment (MIDAS) Questionnaire

mMIDAS questions

Please answer the following questions about ALL of the headaches you have had over the Last 1 month. Select your answer in the box next to each question. Select zero if you did not have the activity in the last 1 month.

_____ 1. On how many days in the last 1 month did you miss work or school because of your headaches?

_____ 2. How many days in the last 1 month was your productivity at work or school reduced by half or more because of your headaches? (Do not include days you counted in question 1 where you missed work or school.)

_____ 3. On how many days in the last 1 month did you not do household work because of your headaches?

_____ 4. How many days in the last 1 month was your productivity in household work reduced by half or more because of your headaches? (Do not include days you counted in question 3 where you did not do household work.)

_____ 5. On how many days in the last 1 month did you miss family, social or leisure activities because of your headaches?

_____ Total (Questions 1-5)

Scoring:

The mMIDAS total score is the sum of the number of days from question 1 to 5.

In order to assign disability grades, multiply the total score on the MIDAS by 3 and then assign the grade based on following table.

MIDAS Grade	Definition	MIDAS Score
I	Minimal or infrequent disability	0 - 5
II	Mild or infrequent disability	6 - 10
III	Moderate disability	11 - 20
IV	Severe disability	21 and over

MIDAS absenteeism domain score is the sum of the number of days from questions 1, 3 and 5.

MIDAS presenteeism domain score is the sum of the number of days from questions 2 and 4.

Missing data:

We score the instrument if 3 out of 5 questions are scored. We do not allow skip patterns so only 4 and/or 5 can be missing in order to calculate mMIDAS total score. If question 4 and/or 5 are missing, then use the number from 2 to impute into 4 and a mean from 1 and 3 for 5.

5.8.4 Beck Depression Inventory -II (BDI-II) scoring

Beck Depression Inventory – II (BDI-II)

This instrument consists of 21 items, each with 4 or 6 statements regarding symptoms of depression. One statement is selected for each item. Each statement has an associated value. Two of the items' values are recoded for scoring, while the others retain their original value.

Group	Original value	Rescored value
1 – 15, 17, 19 – 21	0	0
	1	1
	2	2
	3	3
16, 18	0	0
	1	1
	2	1
	3	2
	4	2
	5	3
	6	3

Score

A single score is calculated by adding up the (rescored) values of the 21 items. The range of values is 0 – 63.

Missing values:

If more than 2 items have missing values, the total BDI score will be missing. If one or two items are missing, their score can be imputed with the mean of the non-missing scores before summing.

Interpretation:

0 – 13: minimal depression
14 – 19: mild depression
20 – 28: moderate depression
29 – 63: severe depression

[figure not shown]
Missing data:

If more than 2 items have missing values, the total BDI score will be missing. If one or two items are missing, their score can be imputed with the mean of the non-missing scores before summing.

5.9 Appendix E: MMD derivation, exceptions

[figure not shown]
5.9.1 Assigning Headache and Migraine Days to Events Spanning Midnight

The diagram below shows all of the possible scenarios for time-based determination of assignment of events to days when the events span midnight.

Example

A headache starts 20 minutes before midnight (Day 1), a triptan is taken at 15 minutes after the midnight (Day 2).

In this case, the midnight Scenario 5 is applied so that Day 1 will be counted as headache/migraine day only.

5.9.2 Spanning Midnight Rules for Multi-Day Events Longer Than Two Days

When an event spans two or more full days, with “tail” conditions (event lasts for less than 4 hrs or less on one side of midnight or the other), the “tail” conditions must be checked separately at each end of the event (beginning and end) to determine which days are included in the event expanse.

Example

A headache event starts 2 hrs before midnight (Day 1), extends across a full day (Day 2), and ends 3 hrs after the next midnight (Day 3).

In this example, because the midnight scenario between Day 1 and Day 2 (Scenario 6) determines that Day 1 will NOT be counted as a headache/migraine day, and the midnight scenario between Day 2 and Day 3 (Scenario 2) determines that Day 3 will NOT be counted

as a headache/migraine day, the event that started on Day 1 and ended on Day 3 will only count as a headache/migraine day on Day 2.

6 Reference

Headache Classification Committee of the International Headache Society (IHS, 2013), The International Classification of Headache Disorders, 3rd edition (beta version), *Cephalgia* Vol. 33(9) 629–808.

Koch G. G., Amara I. A., Davis G. W., and Gillings D. B. (1982). A review of some statistical methods for covariance analysis of categorical data, *Biometrics*, 38(3), 553–595.

Koch G. G., Carr G. J., Amara I. A., Stokes M.E., and Uryniak T. J. (1990). Categorical Data Analysis, *In Statistical Methodology in the Pharmaceutical Sciences*, Ed. by Berry DA. New York: Marcel Dekker, 291–475.

Lehmann, E. L. (1975). Nonparametrics: Statistical Methods Based on Ranks, *San Francisco: Holden-Day*, 132-137, 145.

Schafer, J. L. (1997). Analysis of Incomplete Multivariate Data, *New York: Chapman and Hall*.

Van Elteren, P. H. (1960). On the combination of independent two-sample tests of Wilcoxon, *Bulletin of the International Statistical Institute*, 37, 351-361.

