### 8.3.1 Migraine Days

A migraine day is defined as any calendar day in which the subject experiences a qualified migraine headache (onset, continuation, or recurrence of the migraine headache). A qualified migraine headache is defined as a migraine with or without aura, lasting for **≥ 4 continuous hours**, and meeting at least one of the following criteria:

1.  $\geq 2$  of the following pain features:

- Unilateral
- Throbbing
- Moderate to severe
- Exacerbated with exercise/physical activity

2.  $\geq 1$  of the following associated symptoms:

- Nausea and/or vomiting
- Photophobia and phonophobia

If the subject took **ANY acute medication** (simple analgesics [NSAIDs, acetaminophen], combination analgesics, triptans or ergot-derivative) during aura, or to treat a **moderate or severe headache** on a calendar day, then it will be counted as a migraine day regardless of the duration and pain features/associated symptoms. A migraine headache event that is lasting less than 24 consecutive hours in duration, regardless whether or not it extends into the prior or next

calendar day for less than 4 hours, should be counted as a single migraine day, even if acute medication is taken on the prior or next calendar day. Opioid-containing analgesic and butalbital-containing analgesics are excluded in allowed acute medication categories.

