### **8.5 Additional assessments**

#### **8.5.1 Clinical Outcome Assessments (COAs)**

Clinical Outcome assessments (COAs) will be collected by subjects using a handheld electronic diary (eDiary) at various frequencies during the **double-blind treatment period**.

The eDiary will collect the following COAs daily, at home:

- Date and time of start of headache (i.e. migraine or non-migraine headache)
- Date and time of end of headache
- [REDACTED]
- Pain features (e.g. one-sided, throbbing, worsens with exercise/physical activity)
- Symptoms (e.g. aura, nausea, vomiting, photophobia, phonophobia)
- Use of acute headache medications (medication name [from pre-entered list], date of dosing, number of times taken of each date, number of units taken)

The eDiary will categorize headache events as migraine days or headache days based on the definitions below:

- Headache Day: Any calendar day in which the subject experiences a qualified migraine or a non-migraine headache (initial onset, continuation, or recurrence of the headache lasting  $\geq 4$  continuous hours, or a headache of any duration for which acute medication was administered for treatment of headache pain). A headache event that is lasting less than 24 consecutive hours in duration, regardless if it extends into the prior or next calendar day for less than 4 hours even if acute medication is taken on the prior or next calendar day, should be counted as a single headache day.

- Migraine Day: see [Section 8.3.1](#) for details.

The site study staff will train the subject on how to use the eDiary (e.g. turning on/off, charging, navigating screens, transmitting data, contacting the help desk for technical assistance) and complete the questions. The subject will be instructed to interact with the eDiary every day during the baseline period and treatment period and to bring the eDiary to every study visit. At the Day 1 study visit, the investigator will use the subject's eDiary device to review all data entered during the baseline period and confirm the relevant inclusion and exclusion criteria. Please refer to the eDiary manual for additional details.

During the COVID-19 pandemic that limits or prevents on-site study visits, COA information may still be collected using the eDiary.

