5.1.5 Other imputations

5.1.5.1 eDiary data

The eDiary includes the following clinical outcome assessments:

- Incidence of headache (i.e., migraine with or without aura or non-migraine headache)
- Time of onset of headache
- Time of resolution of headache
- Pain severity per headache
- Symptoms (e.g., nausea, vomiting, photophobia, phonophobia)
- Presence of aura
- Acute medication taken to treat headache, aura-only event, or both headache and aura

As well as, subject-reported outcomes (PROs) measures of [REDACTED], modified MIDAS, [REDACTED], [REDACTED]

Missing eDiary data in the calculation of monthly measurements about subjects' migraine and non-migraine headaches will be handled using the following method:

1. For monthly intervals with ≥ 14 days of eDiary days (including retrospective eDiary days) in each interval:
 - a. Monthly frequency measurements (including migraine days, [REDACTED], migraine attacks, acute medication use, acute migraine specific medication use etc.) will be prorated to 28-day equivalents. Prorated result does not need to be rounded.
[REDACTED]
2. For monthly intervals with < 14 days of eDiary use (including retrospective eDiary days), all monthly measurement will be set as missing and will be handled as described in [Section 5.1.5.3](#).

Briefly, handling missing and incomplete eDiary data is summarized by next rules:

Monthly Endpoint	Condition	Proration Method (does not need to be rounded)
------------------	-----------	--

Monthly frequency measurements (including migraine days, [REDACTED] acute headache medication treatment days)	If diary days in entire baseline or interval post baseline ≥ 14 (including retrospective eDiary days), then do proration; Else monthly measurement is set to missing [diary days is a day with all headache related questions completed retrospectively or not]	Number of observed migraine days * 28/ Number of information days in interval [information day is a diary day or headache day]
[REDACTED]	[REDACTED]	[REDACTED]

Missing PROs [REDACTED] mMIDAS [REDACTED] scheduled to be collected at office visit at certain assessment will not be imputed.

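### The SAP's midnight rule counts its own 29-hour example as 1 migraine day where the protocol's definition gives 3, and the SAP declares no departure

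*SAP*

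**What the plan says.** **Protocol.** Section 8.3.1 defines a migraine day as "any calendar day in which the subject experiences a qualified migraine headache (onset, continuation, or recurrence of the migraine headache"). A headache qualifies if it lasts at least 4 continuous hours and has the listed features or symptoms. One exception deals with short portions across midnight. It begins "A migraine headache event that is lasting less than 24 consecutive hours in duration" and collapses such an event to one day when it runs into a neighbouring day for less than 4 hours. Section 8.5.1 gives headache days a matching exception with the same limit: "A headache event that is lasting less than 24 consecutive hours in duration".

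**SAP.** Section 2.1.4.1 repeats the general definition, leaves out the sentence about events under 24 hours, and refers the reader to an Appendix 5.10 for exceptions. There is no 5.10. The exceptions are in 5.9, headed "MMD derivation, exceptions". Section 5.9.2 checks each end of a multi-day event for a short tail. Its example "starts 2 hrs before midnight (Day 1), extends across a full day (Day 2), and ends 3 hrs after the next midnight" and is resolved so that "the event that started on Day 1 and ended on Day 3 will only count as a headache/migraine day on Day 2". Section 4, which lists changes to the protocol's analyses, records none.

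**The concern.** The SAP applies a tail exception to events that the protocol's exception excludes by its own terms. Where the two documents meet the same diary record, they give different numbers of migraine days.

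MMD is the primary variable. It also supplies the baseline covariate in the primary model and determines who is a 50% responder. As written, the variable to be analysed is not the one the protocol defines, and a reader who relies on SAP Section 4 would not know it.

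Eligibility is also exposed. Inclusion criterion 5 uses the eDiary calculation, and protocol 8.5.1 says the eDiary classifies days by the protocol definitions. SAP 2.1.4.1 has the analysis team derive the endpoints. The count used at screening and the analysed baseline count could therefore differ for the same diary.

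**Working it through.** **1. The SAP's own figure.** Inputs from SAP 5.9.2: 2 h on Day 1, 24 h on Day 2, 3 h on Day 3. Duration = 2 + 24 + 3 = 29 h. Dropping an end day with less than 4 h removes Days 1 and 3 and leaves Day 2. The count is 1, as the SAP states. Setting the cut-off at 4 h or less gives the same result.

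**2. The same event under protocol 8.3.1.** Assume it is a qualified migraine. There is onset on Day 1 and continuation on Days 2 and 3. The exception needs a duration under 24 h, and 29 h does not meet it. The count is 3.

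**3. General shape.** Let the first-day tail be a hours, the last-day tail b hours, with k full calendar days between.
- Duration = 24k + a + b. For k ≥ 1 this is at least 24 h, so the protocol's exception never applies.
- The protocol count is k + 2. The SAP count is k if both tails are short and k + 1 if one is.
- With k = 1 and both tails under 4 h, the event lasts between 24 and 32 h and counts 3 against 1. With one short tail it counts 3 against 2.

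The loss is 1 or 2 days per event, unless another rule restores the tail day, such as the rule on acute medication.

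**4. Effect on MMD.** SAP 5.1.5.1 prorates as "Number of observed migraine days * 28/ Number of information days in interval". The loss in that month's MMD is days lost × 28 / information days, provided the tail days have diary entries.

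| Information days | 2 days lost | 1 day lost |
|---|---|---|
| 28 | 2.0 | 1.0 |
| 23 (minimum for baseline compliance) | 2.43 | 1.22 |
| 14 (minimum for proration) | 4.0 | 2.0 |

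The 14-day row can arise only after baseline, because eligibility requires 23 of 28 diary days at baseline.

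**5. Effect on responder status.** These are assumed patients with 28 information days in each period. L is the number of events with one full day and two short tails. S is the number of one-day events. Protocol MMD = 3L + S; SAP MMD = L + S.

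| (L, S) at baseline, then weeks 9–12 | Protocol | SAP |
|---|---|---|
| (1, 13), then (0, 8) | 16 to 8, −50.0%, responder | 14 to 8, −42.9%, non-responder |
| (1, 12), then (1, 5) | 15 to 8, −46.7%, non-responder | 13 to 6, −53.8%, responder |

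Both baselines have at least 8 migraine days under either rule. The requirement of 15 headache days is met from these events alone under the protocol count (16 and 15). Under the SAP count (14 and 13), further non-migraine headache days would have to be assumed.

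**The case against.** **The exception is written down in advance.** SAP 2.1.4.1 points to exceptions beside the definition, and the appendix title calls them exceptions. This stands in part: the rule is pre-specified. But the pointer goes to a section that does not exist, nothing there says the rule departs from the protocol, and Section 4 says there is no change.

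**The scenario diagram is not reproduced in the text available.** The conditions attached to each scenario cannot be seen, so counts beyond the worked example extend the stated rule. That is a fair limit on step 3. It does not touch the example, whose result the SAP gives in words.

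**A day might need 4 h of headache to count.** That reading would bring the protocol to 1 day. However, protocol 8.3.1 puts the 4-hour requirement on the headache, not on each calendar day.

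**The rule's scope is unclear.** The trigger reads "When an event spans two or more full days", while the example has one full day. Read literally, the trigger would exclude the example, yet the conflict would remain: for k ≥ 2 with two short tails the counts are k + 2 and k. The section heading, about events longer than two days, is more arguable because the example touches three calendar days. This is an editorial point.

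**No effect on the trial's conclusion is shown.** This stands. The rule applies equally to both arms and to baseline, and the responder examples are placed near the 50% threshold on purpose.

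**Conclusion.** The concern holds. For its own 29-hour example the SAP counts 1 day. The protocol gives 3 if the event is a qualified migraine, and the SAP does not declare the difference.

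The worked example is certain. The extension to other long events rests on the tail rule as 5.9.2 words it. An affected event loses 1 or 2 migraine days, worth 2.0 MMD for two lost days with 28 information days and up to 4.0 with 14. One such event in a period can move a patient across the 50% threshold in either direction.

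No bias toward an arm is shown. Without the frequency of such events, the effect on mean MMD or on the treatment difference cannot be computed. This should be fixed because it leaves the primary variable with two definitions.

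**What to change.** Before unblinding, reconcile SAP 5.9.2 with protocol 8.3.1 and 8.5.1 in one of two ways.

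1. **Bring the SAP to the protocol.** Limit the tail rule to events under 24 consecutive hours. Section 5.9.2 then drops no tail day from an event that contains a full calendar day. Cost: SAP wording and a check of the derivation program, including whether headache-day flags come from the eDiary or from the analysis team.
2. **Keep the SAP rule.** Amend protocol 8.3.1 and 8.5.1, declare the departure in SAP Section 4, and run the protocol rule as a sensitivity analysis of the primary and 50% responder endpoints. Cost: a protocol amendment, a Section 4 entry and one extra derivation run for two endpoints.

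A Section 4 entry alone would end the silence but leave the two documents with different definitions of the primary variable.

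Either way, make the heading and trigger of 5.9.2 agree with its one-full-day example, and correct the references to Appendix 5.10. Neither option needs new data.
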